## **6. STUDY PROCEDURES:**

**Social influence campaign:** Individuals living in the 5 intervention arm districts will potentially be exposed to the enhanced social influence strategies. This will include both static ads and video content which will be posted on social media platforms during the duration of the 12-month CRT. The second layer of the campaign will include additional interventions including PrEP champions who will be based at venues where FSW/AGYW work or socialize. Given that randomization is occurring at the programme site and ward levels, service users and their families, peers, and partners will not all be exposed to the campaign given we are not randomizing at the individual level.

**Cross-sectional survey:** Recruitment details are described above. Following completion of the informed consent process, all eligible and enrolled cross-sectional study participants will be asked to participate in a brief 20-30 minute survey. The survey will collect very minimal information related to individual behavior, but will assess PrEP knowledge and attitudes, exposure to PrEP promotion events and the social media campaign, as well as the young woman's views on partner, family and peer perceptions of PrEP. No biological assessments will be performed and no identifying information will be collected from the participants. The trained research assistants will administer the survey on a tablet, reading each question aloud and recording all participant responses. The age of the young woman and the location that the survey was conducted at will be collected.

**Assessment of PrEP programme data:** Participants will not undergo any procedures and no individuals will be recruited for this element. Programme monitoring and evaluation staff will support with providing routinely collected, de-identified programme data for assessment of PrEP initiations and follow-ups completed during the 12-month CRT period.

**Social media metrics:** Participants will not undergo any procedures and no individuals will be recruited for this activity. Aggregate and anonymized data will be collected through social media

metrics in line with each platform's respective privacy policy. Additional data shared through comments or posts onto the website will be categorized and if publicly shared may be used for analysis; privately sent messages, information and information identifying individuals will not be used.

**Table 2. Number and type of study visits and/or contacts**

	Number and type of study visits	Length of each study visit	Where they will take place
Social influence campaign	N/A	N/A	N/A
Cross-sectional survey	1 visit (cross-sectional assessment)	20-30 minutes	Private room at the TB HIV Care offices or in a private room at the mobile van or venue where women are accessing services if that is the preference of the participant and confidentiality can be secured
Assessment of PrEP programme data	N/A	N/A	N/A
Social media metrics	N/A	N/A	N/A

Reimbursement of 100 ZAR (~7 USD) for time associated with completing the cross sectional survey will be provided to each survey participant. Each survey with TB HIV Care service users is estimated to last 20-30 minutes and compensation will be given immediately after completion of the survey.

## **7. STATISTICAL CONSIDERATIONS**

Statistical considerations, specifically around sample size and participant recruitment, will ensure the study is able to detect important differences in the outcomes. Moreover, the statistical analysis plan will outline the analyses that will be conducted to address the main aims of the study.

### *A. Randomization*

The 10 districts /sites in which THC provides PrEP will be taken as unit of randomization for the first layer of comparison. Five of the sites will be randomized to the standard of care PrEP promotion arm, and five to the PrEP promotion+enhanced social media campaign arm. Constrained covariate randomization will be applied taking into account the baseline number of annual PrEP initiations, the number of subdistricts within a site, the number of rural subdistricts, mean district HIV prevalence, and program type (AGYW or FSW or a combination of the two).

Within the PrEP promotion+enhanced social media campaign arm, wards will be randomized to 4 sub-arms receiving different combinations of the enhancements described in Table 1. The

randomization will be stratified by site and effort will be made to reduce potential contamination between wards.

All randomization activities will be completed by the team biostatistician who specializes in cluster randomized trials, [name] [name] (Co-Investigator).

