#### **PrEP Social Influence Campaign CRT:**

The CRT under current consideration will compare the existing standardized community engagement model (i.e. PrEP sensitization/promotion) to an enhanced PrEP social influence campaign using different delivery mechanisms. **The primary outcome will be the proportion of FSW/AGYW clients within the TB HIV Care PrEP programme who initiate PrEP among all eligible marginalized young women to whom it is offered.** Secondary outcomes will be differences in knowledge, attitudes and peer influence across arms (described in sections below)

and 1 and 4-month sustained PrEP use among PrEP initiators. The enhanced social media campaign will be implemented for 12-months while the PrEP champion and community mobilization interventions will be implemented for 6-months and will target young women, parents, teachers, peers, and partners. 5 TB HIV Care district sites within the four provinces will be randomized to each arm (10 districts randomized in total).

There will be two main study arms which will be randomized 1:1 at the district level across the 10 sites which span four provinces. **Arm 1** will receive PrEP sensitization per the ongoing programmatic Standard of Care. **Arm 2** will receive the standard of care through the programme per normal, as well as an enhanced social media intervention that will be targeted to the intervention districts. This is feasible because through social media platforms like Facebook, advertisements can be geographically targeted to specific areas. The primary outcome of PrEP uptake will be powered to assess the difference in PrEP initiations across the 10 sites, comparing PrEP uptake numbers in Arms 1 and 2. Additionally, a second layer of enhancement will be layered onto the intervention arms (Arm 2). Thus in addition to the social media campaign, wards from the five intervention districts will be randomly selected to implement: a) Nothing additional; b) Training and support for venue-based PrEP champions; c) PrEP community mobilization teams; d) Training and support for venue-based PrEP champions AND PrEP community mobilization teams. Details are further highlighted in Table 1 below:

Table 1: Intervention activities and CRT plan		
Arm	Name	Description

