#### *C. Statistical Analysis Plan*

Results will be synthesized across the data sources and implementation outcomes, and utilized to assess the reach and effectiveness of social influence campaign strategies. Findings from the review of programme logs, social media metrics, and cross-sectional surveys will be reported. Costing data and ranges of intervention fidelity and penetration parameters will be used to inform programme activities. A comparison of the social influence campaign intervention vs standard of care at achieving PrEP uptake (primary), 1-month PrEP persistence (secondary) and 4-month PrEP persistence (secondary) will be key outcomes. Cluster level proportions of clients within the TB HIV Care PrEP programme who initiate PrEP will be compared between the main study arms using the unpaired t-test after a log-transformation if necessary. A secondary analysis will adjust for residual confounding by age and other individual characteristics through a two-stage logistic regression residuals approach. A similar approach will be used for the secondary outcomes and the comparison between sub-arms within the intervention main arm. Changes in PrEP knowledge, attitudes and social support across intervention and control areas over the two time periods (pre- and post-intervention) will be estimated using a difference in differences approach. Prevalence of PrEP knowledge, attitudes and social support across intervention and control areas over the two time periods (pre- and post-intervention) will be summarized by questions/item. Multivariate analysis will be conducted to generate patterns of responses by theme (e.g. perceptions of PrEP). Changes over time will be analysed using the difference in differences approach that uses suitable regression models (e.g. logistic, linear) to study the effect of time period and study arm, as well as their interaction, on the responses.

Analysis of data will be conducted using STATA Version 15.0.

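### District allocation is constrained on the baseline count of PrEP initiations, but the primary outcome is a proportion, and baseline uptake is neither balanced directly nor named as a covariate

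*Combined protocol and SAP*

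**What the plan says.** Section 7.A (Randomization) allocates ten districts 5 to 5: "Constrained covariate randomization will be applied taking into account the baseline number of annual PrEP initiations". The other constraint variables are "the number of subdistricts within a site, the number of rural subdistricts, mean district HIV prevalence, and program type". The list contains neither a baseline uptake proportion nor its denominator, the number of eligible women offered PrEP.

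Section 4 (PrEP Social Influence Campaign CRT) defines the outcome as a proportion: "The primary outcome will be the proportion of FSW/AGYW clients within the TB HIV Care PrEP programme who initiate PrEP among all eligible" women offered it. Section 5.C repeats that definition for the programme data. A later sentence in section 4 is looser and speaks of "comparing PrEP uptake numbers in Arms 1 and 2".

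Section 7.C settles the matter for the analysis. Cluster-level proportions "will be compared between the main study arms using the unpaired t-test after a log-transformation if necessary". The adjusted analysis is described as follows: "A secondary analysis will adjust for residual confounding by age and other individual characteristics through a two-stage logistic regression residuals approach". No district-level baseline value is named in either.

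**The concern.** An initiation count is district size multiplied by uptake. A large district with low uptake and a small one with high uptake can have the same count, so a split can be balanced on volume and unbalanced on the quantity that will be tested. There are only ten clusters and one draw. The primary test is unadjusted, and the adjusted analysis names individual characteristics only. If the higher-uptake districts fall in one arm by chance, nothing in the plan is aimed directly at that imbalance. At stake are the precision of the main comparison and how far a reader will trust a difference between two groups of five districts.

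**Working it through.** **Inputs from section 7.B.** 5 clusters per arm; uptake 5% versus 15%; CV k = 0.25 to 0.4; m = 500 to 1000 eligible women per region per year; alpha 0.05 (two-sided assumed); stated power 87% at k = 0.4.

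**Step 1: the plan's own figure.** Power = Φ(√[(c−1)(p1−p0)² / V] − 1.96), with V = p0(1−p0)/m + p1(1−p1)/m + k²(p0² + p1²). At m = 750:
- V = 0.0475/750 + 0.1275/750 + 0.16 × 0.025 = 0.00423
- √(4 × 0.01/0.00423) = 3.07
- power = Φ(1.11) = 86.7%

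It is 85.8% at m = 500 and 87.2% at m = 1000. The 87% reproduces. The formula has no term for the constraint, so the choice of constraint variable cannot alter it.

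**Step 2: can volume balance while uptake does not?** Stay within 500 to 1000 women. Five districts of 500 at 10% give 5 × 50 = 250 initiations. Five districts of 1000 at 5% also give 5 × 50 = 250. Volume is identical and mean uptake differs by 5 points, half the planned effect. This shows that the imbalance is possible, not that it is typical.

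**Step 3: typical imbalance in baseline uptake.** Assume baseline mean uptake of 5%. With simple randomisation at CV 0.4, the SD of the arm difference is 0.4 × 5 × √(2/5) = 1.26 points. Next, enumerate all 252 splits and keep the best 10% or 25% on the count alone (assumed cut-offs, single constraint):

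| Women per district | Correlation of count with uptake | SD, points | 95% of differences within |
|---|---|---|---|
| 500–1000 (plan) | 0.87 | 0.60–0.64 | about 1.2 |
| 500–5000 (assumed) | about 0.46 | 1.09–1.12 | 2.1–2.2 |
| 200–10,000 (assumed) | about 0.29 | 1.18–1.19 | 2.3 |

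The count halves the imbalance under the plan's size range and does little when sizes vary tenfold or more.

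**Step 4: effect on the follow-up comparison.** Step 3 flatters any constraint, because the trial compares follow-up uptake, follow-up carries binomial error, and section 7.A constrains on five variables. At 5% of 750 women the sampling error per district is √(0.05 × 0.95/750) = 0.8 points, against a true between-district SD of 0.4 × 5 = 2.0. The table gives the SD of the arm difference under no effect, in points, with binomial noise, 500 to 1000 women, CV 0.4, the best quarter of splits kept and four further covariates simulated as independent (assumed). The baseline to follow-up correlation is also assumed.

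| Correlation | Constrain on count | Constrain on proportion instead | Count, then adjust for baseline uptake |
|---|---|---|---|
| 0.5 | 1.31 | – | 1.29 |
| 0.7 | 1.27 | 1.23 | 1.15 |
| 0.9 | 1.18 | 1.11 | 0.90 |

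Changing the constraint variable gains 1.27 − 1.23 = 0.04 and 1.18 − 1.11 = 0.07 points. Adjustment gains 0.12 and 0.28.

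**Step 5: net of the lost degree of freedom.** The 5% critical t value rises from 2.306 (8 df) to 2.365 (7 df). A rough half-width, SD × t, goes:
- at 0.7, from 1.27 × 2.306 = 2.93 to 1.15 × 2.365 = 2.72
- at 0.9, from 1.18 × 2.306 = 2.72 to 0.90 × 2.365 = 2.13
- at 0.5, from 1.31 × 2.306 = 3.02 to 1.29 × 2.365 = 3.05, which is no gain

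**The case against.** The strongest reply is that the count is adequate under the plan's own inputs. If districts lie within 500 to 1000 women, it correlates 0.87 with uptake and halves the baseline imbalance. Programme type and number of subdistricts, which are also constrained, should take up some of the size variation. Once noise and all five constraints are modelled, replacing the count by the proportion gains well under 0.1 point of SD against a 10-point planned effect. All of this stands, and it is why the count should stay and why the gain lies mainly in the analysis.

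The reply depends on the narrow size range, which the documents do not secure. Ten districts of at most 1000 women at 5% give at most 500 initiations a year, whereas section 2 reports more than 20,000 women initiated (possibly cumulative) and section 4 over 33,000. Those figures concern level, not spread, but they make the 500 to 1000 range hard to rely on. By section 5, three districts run both programmes and seven run one.

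A second reply is that the looser wording about uptake numbers makes a count the relevant quantity. The stated outcome definition and the test in section 7.C are both in proportions, so it does not.

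A reader might also infer that the trial is biased, or underpowered, because of the constraint chosen. The documents do not support either. Allocation remains random, between-district variation is the error term of the planned t-test, and the 87% takes no credit for any constraint.

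**Conclusion.** The mismatch is real: the plan balances a count, tests a proportion, and names baseline uptake nowhere in the allocation or the analyses. The consequence is some lost precision and credibility with ten clusters. It is not systematic bias, and no stated operating characteristic fails. It would be too strong to say that the count gives no protection. It is a fair proxy at 500 to 1000 women per district and a poor one only if sizes vary much more, which the documents neither show nor exclude.

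Under the plan's range and CV 0.4, adjusting for baseline uptake lowers the null SD by about 9% at correlation 0.7 (1.15/1.27 = 0.91) and 24% at 0.9 (0.90/1.18 = 0.76). These figures rest on the assumed correlations, 5% baseline uptake and independence of the other four constraint variables. A residual chance difference of one to two points is small against a 10-point effect, but would matter more if the true effect is smaller.

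**What to change.** First confirm that the pre-launch programme logs give, by district, the number of eligible women offered PrEP on the same definition as the outcome. Section 5.C describes such logs for the campaign period only, and section 7.A documents only the initiation count at baseline. If they do:

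1. In section 7.A, add the district's baseline uptake proportion (initiators divided by eligible women offered PrEP before launch) to the constraint variables. Keep the count as well.
2. In section 7.C, prespecify that proportion as the single cluster-level covariate in the secondary adjusted analysis, for example by regressing the ten district residuals on arm and baseline uptake.
3. If the districts are already drawn, make change 2 only.

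The cost is one tabulation of existing logs, two short wording changes and one residual degree of freedom (8 to 7). If the baseline to follow-up correlation is about 0.5 or lower, the adjustment gains little or nothing, so it belongs in the secondary analysis and the primary t-test can stay as planned. If the logs do not hold the denominator, state this as a limitation.

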#### *B. Sample Size Considerations*

**Social influence campaign (CRT):** The primary outcome for this study will be PrEP uptake within the TB HIV Care programme. Each of the 10 cities in which TB HIV Care provides PrEP will be included as clusters. Assuming between 500 and 1000 PrEP-eligible women reached by the TB HIV Care PrEP programme per geographic region annually, we considered a coefficient of variation (CV) ranging from 0.25 to 0.4, and a minimum improvement in uptake of 10 percentage points (5% to 15%). With a conservative CV of 0.4, 5 clusters per arm will provide 87% power to detect this difference at an  $\alpha=0.05$  level of significance. For the second layer of randomization for enhanced social influence activities, a total of 216 wards (a smaller unit of subdivision used in South Africa to divide regions for political and administrative purposes) exist across the 5 intervention sites, which will be randomized across four sub-arms. There will be roughly 54 wards per sub-arm each with at least 10 PrEP-eligible women. Overall, arm 2 is hypothesized to have PrEP initiations of 15% where the least effective sub-arm [no additional enhancement] has an uptake rate of ~10% and the most effective sub-arm [2d which combines PrEP champions and PrEP community mobilization will have] will have an uptake rate of up to ~20%. Having at least 30 venues per sub-arm would provide 84% power, at a 5% level of significance, assuming a conservatively high CV of 0.4, to detect this difference. As this will be an exploratory investigation, the emphasis will be on the additional yield by the enhancements and thus no correction for the multi-arm hypothesis testing will be conducted.

**Cross-sectional survey:** In order to assess the penetration of exposure to the intervention and thus yield insights into the mechanism of intervention effect (or lack thereof), we are assessing changes in PrEP knowledge and community attitudes over time. Given that awareness to PrEP and attitudes may change over time independent of the intervention, we have included both intervention and control sites pre- and post- intervention in order to compare differences in awareness and attitudes over time between the intervention and control sites. Cross-sectional surveys will be administered across 3 intervention and 3 control sites pre- and post-CRT implementation. With 100 surveys being conducted per site per timepoint, we will collect a total of 1200 survey responses across the 6 selected sites (600 pre-intervention and 600 post-intervention). When selecting the 6 sites for survey implementation, programme type (FSW vs. AGYW vs. both) will be accounted for and from there a random sample will be drawn. With 100 women included per site, there will be a sufficient number of women to account for heterogeneity across sites and will ensure sufficient representation across both intervention and control sites, but will also allow for 300 combined FSW/AGYW before and 300 combined FSW/AGYW after intervention in the intervention arms, which will allow for further assessment of the impact of the additional layered strategies (PrEP champions and community mobilization) on modifying the effect of the social media campaign on PrEP uptake.

**Social media metrics:** No sampling plan needed; these will be process indicators used to evaluate engagement with the social media campaign (intervention activities).

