Currently TB HIV Care is implementing large scale PrEP programmes for FSW and AGYW across four provinces (KwaZulu-Natal, Mpumalanga, Eastern Cape and North West Province) in South Africa. PrEP is provided by professional nurses at drop-in centres and mobile vans – implemented largely within communities. As such, TB HIV Care will lead the cluster randomized trial and data collection within the existing programme sites. TB HIV Care has extensive experience working with FSW and AGYW, as they have been providing HIV prevention services, including HIV testing and counseling, sexually transmitted infection screening and treatment, and condom provision to marginalized young women since 2012 through the mobile van health clinics and drop-in centre wellness clinics. PrEP service delivery for FSW across TB HIV Care supported sites in South Africa began in 2016, expanding in line with DOH priorities to AGYW in 2018 (mobile teams, community outreach, staff placement at DOH clinics). The TB HIV Care programme is funded through 2024 and had already initiated >20,000 women on PrEP in 2020. As the programme evolves, so do the interventions to support sustained PrEP uptake. The services for women are provided through both the FSW and AGYW programmes which have substantial areas of overlap. Programmatic data from TB HIV Care reinforce earlier results from South Africa that PrEP uptake among young women is relatively low, and PrEP use falls by nearly half at 1-month, continuing a steep decline until 7-months. Challenges in PrEP uptake and persistence are similar across sites. These data highlight the potential impact of this research to rigorously evaluate PrEP implementation strategies to initiate and maintain young women on PrEP during periods of heightened HIV risk as the programme continues to expand in coming years.

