#### **4. STUDY DESIGN:**

This grant combines evaluation of ongoing PrEP programme implementation (previous work) with modified, programme informed implementation strategies for testing through two short-duration cluster randomized trials (CRTs). Specifically, this study protocol is focused on PrEP programme optimization through modifying the implementation strategies of ongoing programmatic activities by adjusting the delivery modalities and actors promoting PrEP within the community. The effect of these modifications on PrEP uptake (primary outcome) and continuation (secondary outcome) will be tested using an initial CRT. A second CRT focused primarily on PrEP continuation (retention) will be included in a separate, future protocol.

TB HIV Care is a South African non-profit organization that works directly with the Department of Health as the country's largest PrEP provider for AGYW and FSW. TB HIV Care has initiated over 33,000 women at high risk for HIV infection on PrEP, and has 13 active sites as of 2021. Of note, these are two PrEP programmes that are run by TB HIV Care (8 of the 13 active sites are part of the FSW programme and 5 of the 13 active sites are part of the AGYW programme). **The proposed study design leverages a cluster randomized trial design as some intervention components may not be feasibly randomized at the individual-level (e.g. PrEP peer ambassadors operating within venues/community locations, community mobilization and social media ads).** This trial is feasible given the short duration of the outcomes measured (PrEP uptake and 1- and 4-month PrEP persistence) and utilization of routine programme data for primary outcome ascertainment, and the testing is an adaptation of existing interventions. Based on the programme team's experience and PrEP barriers literature, this first CRT will focus on generating sustained PrEP demand, but also destigmatizing PrEP within young women's social environments (e.g. family, friends, partners). **CRT1 is described within this application.** The second CRT will likely optimize peer support mechanisms during the early days of PrEP use, but this will be refined in late 2022 based on the programme's input and a separate protocol will be submitted surrounding CRT2.

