## **5. STUDY POPULATION:**

The study population includes female sex workers (FSW) and adolescent girls and young women (AGYW) who will participate in the TB HIV Care programme over a one year period (12-months) across multiple sites starting at the launch of the campaign. Overall, since programme inception, TB

HIV Care has implemented PrEP services for women in 17 sites across 6 provinces. Currently 13 sites are actively implementing PrEP programming in 10 districts across 4 provinces and will contribute to the CRT aggregate level data: OR Tambo, Eastern Cape (AGYW & FSW); Zululand, KZN (AGYW); uThukela, KZN (AGYW); uMgungundlovu, KZN (AGYW & FSW); eThekwi, KZN (AGYW & FSW); Ehlazeni, Mpumalanga (FSW); Gert Sibande, Mpumalanga (FSW); Nkangala, Mpumalanga (FSW), [name], North West Province (FSW); and Ngaka Modiri Molema, North West Province (FSW). Here, participation is defined as receiving  $\geq 1$  of the following HIV prevention services offered to FSW and AGYW by TB HIV Care: STI screening and/or treatment, pregnancy testing, HIV testing, or any other service that would result in having a health screening form on file. All clients seen by TB HIV Care are assigned to HIV acquisition risk groups (FSW, AGYW, or others) the first time they are seen based on risks reported on a standardized intake form. Women screening positive for HIV on their first encounter with the programme during the study period will be excluded.

The time period of interest will be 12-months. We anticipate the social media campaign to launch in February 2022, in which case the study period would be February 1, 2022-January 31, 2023. The one year of follow-up will begin at the time of campaign launch.

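### The 500-1000 women and 5% uptake behind the 87% power imply 25-50 initiations per district-year, which is hard to reconcile with the protocol's own PrEP counts; the documents do not show which input is off or whether power changes

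*Combined protocol and SAP*

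**What the plan says.** Section 7.B (Sample Size Considerations) sets the main comparison at 5 districts per arm, uptake of 5% against 15%, a between-cluster CV of 0.4 (range considered 0.25 to 0.4) and a 5% significance level, and states 87% power. The cluster size is given as "Assuming between 500 and 1000 PrEP-eligible women reached by the TB HIV Care PrEP programme per geographic region annually". Neither the cluster size nor the 5% has a source, and power for this comparison is shown at one baseline only.

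Elsewhere the protocol describes the size of the same programme:

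- Section 2 says the programme "had already initiated >20,000 women on PrEP in 2020".
- Section 2 also says that "PrEP service delivery for FSW across TB HIV Care supported sites in South Africa began in 2016", with young women added later: "expanding in line with DOH priorities to AGYW in 2018 (mobile teams, community outreach, staff placement at DOH clinics".
- Section 4 says "TB HIV Care has initiated over 33,000 women at high risk for HIV infection on PrEP".
- Section 5 says the provider "has implemented PrEP services for women in 17 sites across 6 provinces", and then "Currently 13 sites are actively implementing PrEP programming in 10 districts across 4 provinces".

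The only description of baseline uptake outside the sample size section is in section 2, without a figure: "PrEP uptake among young women is relatively low". Section 7.A uses each district's annual number of initiations to constrain the randomization but gives no values.

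**The concern.** Women reached multiplied by uptake gives initiations, so the two planning inputs can be checked against the programme's own initiation counts. They fall well short of them.

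All 10 active districts are already in the trial, so clusters cannot be added within the active programme. The sample size paragraph is the document's only support for 5 against 5 districts detecting a 10-point gain. The consequence depends on which input is wrong. Between-district variation dominates the variance, so a larger cluster size barely moves the power. A higher baseline with the same CV and the same 10-point target widens the between-district SD and can lower the power materially. A reader cannot tell which case applies.

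**Working it through.** **1. Reproducing the 87%.** Inputs from section 7.B: c = 5 districts per arm, p0 = 0.05, p1 = 0.15, k = 0.4, m = 500 to 1000. Sidedness is not stated, so I assume two-sided. The Hayes-Moulton formula for unmatched clusters is

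power = Φ( √[ (c−1)(p1−p0)² / V ] − 1.96 ), with V = p0(1−p0)/m + p1(1−p1)/m + k²(p0² + p1²).

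- m = 1000: V = 0.000175 + 0.004 = 0.004175; √(0.04/0.004175) = 3.095; power 87.2%.
- m = 500: V = 0.00435; power 85.8%.

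The stated 87% is reproduced.

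**2. Initiations implied by the plan.** Without the campaign: 500 × 0.05 = 25 to 1000 × 0.05 = 50 per district-year. At the 15% target: 75 to 150.

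**3. Initiations implied by the programme counts, read leniently.** Both counts are taken as cumulative since 2016 and spread over all 17 sites ever run. The years of accrual (5 to the end of 2020, 6 to the end of 2021) are my assumptions.

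- 20,000 / 5 / 17 = 235 per site-year, which is 4.7 times 50 and 9.4 times 25.
- 33,000 / 6 / 17 = 324 per site-year.

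These readings favour the plan in three ways. The young women's programme started only in 2018. Every closed site is credited with the full period. Three of the 10 districts hold two sites, so a per-site figure understates a per-district one. Even so, both figures exceed the 75 to 150 implied at the intervention target.

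**4. What would close the gap.**

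- *Scope:* to come down to 50, the share of initiations outside the trial denominator would have to be 1 − 50/235 = 79%, or 1 − 50/324 = 85%.
- *Reach alone:* at 5% uptake, 235/0.05 = 4,700 and 324/0.05 = 6,480 eligible women per year.
- *Uptake alone:* with 500 to 1000 women, 235/1000 = 24% up to 324/500 = 65%.

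**5. Power if only reach is too low** (5% v 15%, CV 0.4). At m = 10,000 power is 88.4%. As m grows without limit V tends to 0.004, √(0.04/0.004) = 3.162, and power is 88.5%.

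**6. Power if the baseline is higher.** The 10% baseline is illustrative and does not come from the documents; m = 1000.

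| Scenario | V | Power, untransformed |
|---|---|---|
| 10% v 20%, CV 0.4 | 0.00825 | 59.6% |
| 10% v 20%, CV 0.25 | 0.003375 | 93.1% |
| 10% v 20%, planned SDs of 2 and 6 points held | 0.00425 | 86.6% |
| 10% v 30% (threefold ratio kept), CV 0.4 | 0.0163 | 88.0% |

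Section 7.C allows a log-transformation. For that test I took district uptake as lognormal, with log-scale variance per arm s² = ln(1 + k² + (1−p)/(mp)). I used a noncentral t with 8 df and noncentrality [ln(p1/p0) − (s1² − s0²)/2] / √[(s0² + s1²)/5].

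- Planned inputs (5% v 15%, CV 0.4): about 96% at m = 500 and 97% at m = 1000.
- 10% v 20%, CV 0.4: s0² = 0.156, s1² = 0.152, noncentrality 2.80, power 69%. With beta-distributed district uptake, simulation gives about 61%.
- 10% v 20%, CV 0.25: about 96%.

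**7. Baseline at which power for a 10-point gain reaches 80%** (m = 1000). At CV 0.4 this is about 6.3% untransformed and 8.2% on the log scale. At CV 0.25 it is about 14% and 15%.

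**The case against.** The strongest reply is that the only direction the documents favour is harmless. Uptake is described as low, no section gives a baseline above 5%, and an uptake of 24% to 65% would sit badly with that description. This points to understated reach, and planning on too few women per cluster is conservative. The sub-arm calculation in section 7.B also treats its ward size as a floor: 216 wards × 10 women / 5 districts = 432 per district, close to 500. That suggests deliberately low cluster sizes, although the ward figure is itself an unsourced assumption. All of this stands as a reason to lean towards reach. It does not establish it.

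A second reply is that the comparison is indirect. The counts are programme-wide numerators. The trial denominator is eligible women offered PrEP: those aged 15-24 in the young women's programme and sex workers aged 18 or over. The counts may include clients in other risk groups, closed sites, two further provinces, or initiations at health department clinics. That is fair, but it would have to account for 79% to 85% of initiations after closed sites have already been given a full share. No section says it does.

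Three stronger readings are tempting, and the documents support none of them:

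- *The 87% is miscalculated.* It follows from its inputs.
- *The trial is underpowered.* The loss needs a baseline above 5%, a CV near 0.4 and a fixed 10-point target together. Power is 87% or more when the CV is 0.25, the planned SDs are held, or the threefold ratio is kept. On the log scale the starting point is about 96%, not 87%.
- *The programme initiated 20,000 / 10 = 2,000 women per district in 2020 alone, more than all the women assumed reached.* The wording fits a cumulative total equally well, so I put no weight on this figure.

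**Conclusion.** The mismatch holds. The planning inputs imply 25 to 50 initiations per district-year, against about 235 to 324 per site-year on lenient readings of the protocol's counts. Reach, baseline uptake or both are probably misstated, and the documents do not settle which.

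The effect on power is conditional: essentially none (at most 88.5%) if only reach is too low, and possibly material if baseline uptake is above 5% with the 10-point target and a CV of 0.4 kept. The size of that loss depends on the between-district spread and on whether the log-transformation is used.

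The conclusion rests on the assumed years of accrual, on averaging over sites whose volumes will differ, and on the counts mostly covering the trial's own populations. Confidence is high for the mismatch and low for any change in power.

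**What to change.** Before launch, tabulate from the prior year's programme logs, for each of the 10 districts: women eligible and offered PrEP, women initiating, and uptake. Add the between-district SD and CV. The logs already supply the primary outcome (section 5.C), and annual initiations are already needed for the constrained randomization (section 7.A).

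In section 7.B:

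- State whether the 20,000 and 33,000 counts are annual or cumulative, and which clients, sites and provinces they cover.
- Replace the 500-1000, 5% and CV inputs with the tabulated values.
- Restate power, or the minimum detectable difference, for 5 against 5 districts under the test planned in section 7.C, over a range of baselines and CVs.
- Say whether the target is 10 percentage points or a ratio if the baseline is not 5%.

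The cost is one tabulation of existing data and one revised paragraph. Districts, outcome and test are unchanged. The stated power may become less favourable.
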